#### 6.5.3 POPULATION PROFILING PROCEDURES

The procedures to profile the population key characteristics will be:

- i. Demographics and Medical & Ocular History [REDACTED] [REDACTED]
- ii. Habitual contact lenses wearing characteristics;
- iii. [REDACTED]

#### 6.5.4 STUDY MANAGEMENT PROCEDURES

The procedures to ensure that the study protocol is followed will be:

- i. Contact lens fitting as per the Biofinity® multifocal contact lens fitting manual;
- ii. Contact lens fitting as per the MyDay® multifocal contact lens fitting manual;
- iii. Contact lens fit clinical classification;
- iv. Recording of contact lens prescribing time;
- v. Recording of number of contact lenses to arrive to the prescription to dispense;

### 6.6 Study Visit Routine

#### 6.6.1 VISIT 1 – SCREENING ENROLMENT FITTING DISPENSING VISIT

The routine below will be followed:

- Explanation of the study
- Signing of the consent form
- Participant demographics and ocular history questionnaire
- [REDACTED]
- [REDACTED]
- [REDACTED]
- Standard distance visual acuity [REDACTED]
- [REDACTED]
- [REDACTED]
- Review of inclusion and exclusion criteria
- Decision to continue with determination of eligibility
- BIOFINITY® MULTIFOCAL INITIAL CONTACT LENS INSERTION AND WEAR FOR 10 MINUTES
- [REDACTED]
- [REDACTED]
- [REDACTED]
- Study contact lens prescription suitability evaluation & decision to dispense or change contact lens power

- BIOFINITY® MULTIFOCAL REMOVE INITIAL CONTACT LENS & INSERT BIOFINITY® MULTIFOCAL SECOND CONTACT LENS AND WEAR FOR 10 MINUTES  
▪ [REDACTED]  
▪ [REDACTED]  
▪ Standard distance, intermediate and near visual acuity with contact lenses (monocular & binocular)  
▪ [REDACTED]  
▪ [REDACTED]  
▪ Instruction for use  
▪ Study product dispensing  
▪ Scheduling

#### 6.6.2 VISIT 2 – BIOFINITY® MULTIFOCAL CONTACT LENS FOLLOW-UP & MYDAY® MULTIFOCAL CONTACT LENS FITTING AND DISPENSING VISIT (14 ± 3 DAYS AFTER VISIT 1)

The routine below will be followed:

- [REDACTED]  
▪ [REDACTED]  
▪ [REDACTED]  
▪ [REDACTED]  
▪ LogMAR visual acuity measurement at distance, intermediate and near (monocular and binocular)  
▪ BIOFINITY® MULTIFOCAL CONTACT LENS REMOVAL  
▪ [REDACTED] [REDACTED]  
▪ Standard distance visual acuity [REDACTED]  
▪ MYDAY® MULTIFOCAL INITIAL CONTACT LENS INSERTION AND WEAR FOR 10 MINUTES  
▪ [REDACTED]  
▪ [REDACTED]  
▪ Standard distance, intermediate and near visual acuity with contact lenses (monocular & binocular)  
▪ Study contact lens prescription suitability evaluation & decision to dispense or change contact lens power  
▪ MYDAY® MULTIFOCAL REMOVE INITIAL CONTACT LENS & INSERT MYDAY® MULTIFOCAL SECOND CONTACT LENS AND WEAR FOR 10 MINUTES  
▪ [REDACTED]  
▪ [REDACTED]  
▪ Standard distance and near visual acuity with contact lenses (monocular & binocular)  
▪ Study contact lens prescription suitability evaluation & decision to dispense or change contact lens power  
▪ Instruction for use  
▪ Study product dispensing  
▪ Scheduling

 [REDACTED]

[REDACTED]

[REDACTED]

[REDACTED]

[REDACTED]

### 6.6.3 VISIT 3– MYDAY® MULTIFOCAL CONTACT LENS FOLLOW-UP & DISCHARGE VISIT (14 ± 3 DAYS AFTER VISIT 2)

The routine below will be followed:

- [REDACTED]
- [REDACTED]
- [REDACTED]
- [REDACTED]
- [REDACTED]
- LogMAR visual acuity measurement at distance, intermediate and near (monocular and binocular)
- MYDAY® MULTIFOCAL® CONTACT LENS REMOVAL
- Safety ocular integrity
- Standard distance visual acuity [REDACTED]
- Discharge

## 7 SAMPLE SIZE DETERMINATION AND STATISTICAL ANALYSIS

### 7.1 Sample Size Determination

Sample size calculations took into consideration that the two co-primary endpoints to assess contact lens handling, inserting and removal, will be both required to be met at the completion of the study to demonstrate the study hypothesis. Accordingly non-inferiority testing was carried out considering a power of 90% in order to achieve a final power of 80% to test simultaneously the two primary endpoints. No adjustment is required for  $\alpha$ .

The results of a previous study involving similar population which measured contact lens handling (0-100 points visual analogue scale) achieved a standard deviation of the difference between two study contact lenses of 9.6 and 14.7 for insertion and removal respectively [1]. To demonstrate non-inferiority at both insertion and removal, considering a margin of non-inferiority of -7.00 and assuming no difference between test and control, for a one-sided paired t-test with  $\alpha = 2.5\%$  and  $\beta = 10\%$ , 49 participants are required to complete the study as per the protocol.

The reference study being conducted in the USA and involving a slightly different protocol (masked vs. open label) and considering that to be representative of the full range of presbyopes with similar number of young emergent, established and older advanced presbyopes with possible different levels of dexterity, the aim is to achieve a per protocol total population of 60 participants made up of approximately 20 in each of emergent low addition presbyopes (near addition +0.75D to +1.25D), established medium addition presbyopes (near addition +1.50D and +1.75D) and advanced high addition presbyopes (near addition +2.00D to +2.50D).

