## 1 OVERALL SYNOPSIS

Study Sponsor	The Sponsor for this investigation will be CooperVision International Limited (CVIL) [name]. The sponsor contact will be [name].
Title of Study	Refitting Biofinity multifocal contact lens wearer with MyDay multifocal contact lenses.
Protocol Number	EX-MKTG-155 ID23-62
Type of study	The study will be conducted following an interventional, prospective, open label, sequential study design.
Study Population	Required: 60 completed participants as per protocol (cohort) with a minimum of 66 to be enrolled. Planned: Up to 70 screened, with the aim of enrolling 66 participants.
Duration of study treatment	14 (-0/+3) days of daily disposable, daily contact lens wear per study contact lens type.
Inclusion Criteria	
In order to be enrolled, each participant shall meet the following criteria:
 
 
i. Age 40 years and older;
 
ii. Current multifocal contact lens wearer (other than MyDay® multifocal but can include Biofinity® multifocal);
 
iii. Spectacle refraction: Distance: Sphere: -6.00D to + 4.00D Astigmatism: 0.00D to -0.75D Near Addition: +0.75D to +2.50D
 
iv. Best corrected visual acuity of at least 20/25 in each eye.
 
 
The prospective participants will be given a Participant Information Sheet to read and an Informed Consent Form to sign prior to any evaluation.

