### 5.2 Number of Participants

Up to 70 participants to be screened, with the aim to enrol up to 66 participants and with a view to achieve a cohort (participants completing the study as per protocol) sample size of 60 made up of approximately 20 in each of the low (near addition +0.75D to +1.25D), medium (near addition +1.50D and +1.75D) or high (near addition+2.00D to +2.50D) spectacle additions groups. Therefore 66 participants will be enrolled to account for drop out based upon a potential 10% drop out rate, has been determined to be optimal, balancing the need for sufficient discrimination and limiting inconvenience to participants by not inflating the study sample (see section 7.1).

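### Does Section 7.1 misstate the power for meeting both co-primary endpoints by giving 80%?

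*Combined protocol and SAP*

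**What the plan says.** Section 7.1 makes insertion and removal co-primary endpoints that "will be both required to be met at the completion of the study to demonstrate the study hypothesis". It does not adjust alpha, and it sets the power for each endpoint by "considering a power of 90% in order to achieve a final power of 80% to test simultaneously the two primary endpoints". The planning SDs come from an earlier study, which "achieved a standard deviation of the difference between two study contact lenses of 9.6 and 14.7 for insertion and removal respectively". With a margin of -7.00, no true difference and a one-sided paired t-test at 2.5% with beta of 10%, the result is that "49 participants are required to complete the study as per the protocol".

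The section then moves to a larger number: "the aim is to achieve a per protocol total population of 60 participants". Its reasons are that the earlier study was run in the USA and was masked rather than open label, and that the three near-addition groups should be about equally represented. No power is given for 60.

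On enrolment, Section 5.2 says "Therefore 66 participants will be enrolled to account for drop out based upon a potential 10% drop out rate" and describes the plan as "Up to 70 participants to be screened, with the aim to enrol up to 66 participants". The synopsis asks for "60 completed participants as per protocol (cohort) with a minimum of 66 to be enrolled".

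**The concern.** The sentence in Section 7.1 presents 80% as the power to be achieved for the two endpoints together, and it is the only overall power in the plan. A joint power near 80% would be expected only if both endpoints had power close to 90%; if they were independent it would be 0.90 x 0.90 = 81%. The SDs printed in the same section are far apart, so this cannot be the case: a sample that gives 90% for the noisier endpoint gives much more for the other. The section then raises the target to 60 without restating the power.

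If the 80% were a miscalculation, the sample size derived beside it would also be in doubt. If it is merely loose, a reader may underrate the power and may not notice that success rests almost entirely on removal. Beside this, 66 enrolled at 10% drop-out does not quite yield 60 completers, and 66 appears both as a minimum and as an upper limit.

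**Working it through.** **Inputs (Section 7.1).** SD of the paired difference 9.6 (insertion) and 14.7 (removal); margin 7 points; true difference 0; one-sided alpha 0.025; paired t-test. The correlation between the insertion and removal differences is not given, so bounds that hold for any correlation are used.

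**Formula.** For n completers, power = P(T > t(0.975; n - 1)), where T is noncentral t with n - 1 degrees of freedom and noncentrality 7√n / SD.

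**Step 1: the plan's own figure.**
- Removal: n = 48 gives 89.8%. n = 49 has noncentrality 7 x 7 / 14.7 = 3.33 and gives 90.42%. The smallest n for 90% is 49, as stated.
- Insertion: n = 21 gives 88.8% and n = 22 is the smallest that reaches 90%.

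So 49 is right, and removal alone sets it.

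**Step 2: where 80% comes from.** If each endpoint has power of at least 0.90, each fails with probability of at most 0.10, and at least one fails with probability of at most 0.10 + 0.10. Hence the joint power is at least 1 - 0.20 = 0.80 under any correlation.

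**Step 3: joint power on the plan's inputs.** The lower bound is insertion + removal - 1; the upper bound is the smaller of the two.

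| Completers | Insertion | Removal | Both, any correlation |
|---|---|---|---|
| 38 | 99.21% | 81.55% | 80.8% to 81.6% |
| 49 | 99.88% | 90.42% | 90.30% to 90.42% |
| 60 | 99.98% | 95.23% | 95.22% to 95.23% |

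Insertion power is so near 1 that the joint power is essentially the removal power. Simulation of correlated endpoints agrees to within simulation error (40,000 trials per cell, correlations from -0.5 to 0.8): 90.2% to 90.6% at 49 and 95.1% to 95.4% at 60.

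**Step 4: sensitivity.** The values varied here are assumptions, not figures from the plan.

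| Assumed departure | Power at 49 | Power at 60 |
|---|---|---|
| True difference -1 on both scales (joint, lower bound) | 78.9% | 87.2% |
| Removal SD 17, zero difference (removal) | 80.6% | 88.0% |
| Removal SD 18, zero difference (removal) | 76.0% | 84.2% |
| Removal SD 19, zero difference (removal) | 71.5% | 80.2% |

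**Step 5: enrolment.** 66 x 0.9 = 59.4 expected completers; 60 / 0.9 = 66.7; 60 x 1.1 = 66, which is evidently how 66 arose. With independent losses at 10%, the chance of 60 or more completers from 66 is 0.51. Joint power at 59 completers is 94.9%, against 95.2% at 60.

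**The case for a change.** The best case for an edit is that Section 7.1 speaks of a final power to be achieved, not of a minimum, and gives a rule of thumb where its own inputs allow an almost exact answer. A joint power of 80% would need only 38 completers, so the figure describes neither 49 nor 60. One added sentence would show how much reserve the 60 completers hold against the section's own doubts about the earlier study.

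It is true that 80% is not the power implied by the inputs, and that the plan states no power at 60. The conclusion that something must change does not follow:

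- The sentence explains why 90% per endpoint was chosen, and that reasoning is correct. Replacing it would remove a valid justification.
- That removal is the limiting endpoint can be read from the two SDs, which share one margin, alpha and beta.
- A headline 95% would lean on SDs that the section itself says may not carry over. Under the assumed departures in Step 4, power at 49 falls to about 80% or below, and at 60 it approaches 80% at a removal SD of 19. The modest claim is the prudent one.
- The 90% and 95% belong to the paired t-test of Section 7.1. Section 7.2 plans a mixed model with lens, order and their interaction, and these figures were not derived for that model.

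On enrolment, the difference between a minimum of 66 and up to 66 is a real inconsistency. The synopsis also states the aim of enrolling 66, so the intended number is clear.

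**Conclusion.** The concern does not call for a change. The 80% is a valid, conservative floor that follows from sizing each endpoint at 90%; it is not an arithmetic error. The 49 reproduces exactly. Under the stated SDs, zero true difference and the paired t-test, the power to meet both endpoints is about 90% at 49 completers and about 95% at 60, so the stated figure is low by about 10 and 15 points, in the safe direction. Restating it would alter no sample size, analysis or conclusion.

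The drop-out rounding costs about 0.3 points of power (95.2% to 94.9%), and the wording around 66 is a clerical slip. A team that reports the achieved power in the detailed analysis plan still to be written could do so beside the existing sentence, labelled with the paired t-test and its assumptions, but nothing depends on it.

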### 7.2 Statistical Analysis Plan

For all the key parameters recorded, summary tables including descriptive and/or distribution statistics will be given. For continuous and ordinal variables, the following descriptive statistics will be reported: mean, median, standard deviation, minimum, maximum, quartiles and sample size. For ordinal variables, and nominal variables distribution tables will be shown.

The comparison between test and reference contact lenses, in terms of ease of insertion (0-100 VAS) and ease of removal (0-100VAS) will be carried out using Generalized Linear Mixed Model. The model will include

 Eye rinse after ocular evaluation with fluorescein

contact lens (test, reference) and order (Visit1, Visit2) as fixed factor. Their interaction will be included in the analysis. The covariance structure that best models the residuals errors will be selected according to the AICc. The comparison between test and reference contact lens will be carried out using the 95% confidence interval (CI) of the mean difference estimated by GLMM. Non-inferiority will be demonstrated if the 2-sided 95% CI of the mean difference lies entirely above the margin of non-inferiority of -7.0. In the event that non-inferiority is demonstrated testing for equivalence will be carried out.

A detailed statistical analysis plan will be developed prior to database closure.

## 8 RISK ANALYSIS

### 8.1 Benefits

There might not be direct benefits to the participants in this study. However, participation in a study may contribute to scientific research information that may be used to optimise the refitting procedure of multifocal contact lenses. In addition, participants, who all have presbyopia and are current multifocal contact lens wearers, will have the opportunity to try the two contact lens vision alternatives, at no cost to them and identify if they prefer one type vs. the other and / or prefer either type to their own contact lenses. Any participant that prefers one of the two contact lens types to their own and wishes to switch contact lens type will be able to purchase the preferred contact lenses from their own eyecare practitioner at the end of the study.

### 8.2 Risks

All the assessments are routine clinical procedures or more detailed procedures, none presenting any increased risk to participants compared with normal clinical routine.

All participants will be current soft contact lens wearers. The risks of taking part in the study are no greater than those associated with wearing their own contact lenses. The reference and the test contact lenses are CE marked, currently marketed daily disposable contact lenses. The risks associated with wearing the reference and the test contact lenses are similar to wearing any type of approved marketed soft contact lens.

Complications may occur due to non-compliant behaviour. This will be mitigated by the investigator providing the participant with indications for use for the contact lenses prior to dispensing. The participants will be under the care of the research investigators for the four weeks study period and the investigators will be present to deal with any unexpected event.

The participants will have their vision checked at the onset of the study and prior to exiting the study to ensure that their vision remained unchanged.

### 8.3 Conclusion

OCULAR TECHNOLOGY GROUP - International has determined that the proposed clinical investigation, based on the users and products effectiveness risks and the risk management strategy in place (preventative and corrective), given that the severity of problems will be mostly minor, non-permanent and the likelihood of occurrence is unlikely with likelihood of non-detection if problem occurs being low, this study is justified as the overall potential benefit to the population outweighs its risks.

## 9 ADVERSE EVENTS AND REPORTING

### 9.1 Adverse Events

Adverse events including serious adverse events and quality complaints will be reported in accordance with ICH E6 Guideline for Good Clinical Practice. Adverse event reports to the Independent Ethics Committee and MHRA will be made according to their requirements.

### 9.1.1 ADVERSE EVENT DEFINITIONS

An 'adverse event' refers to any undesirable clinical occurrence in a participant, whether it is considered to be device-related or not.

Disease signs and symptoms present prior to the study product being utilised are not considered AEs, unless the condition re-appears or worsens in intensity or frequency during the study.

Adverse events (AE) may be classified as 'unanticipated adverse device effects,' 'serious adverse events,' 'significant adverse events,' or 'non-significant adverse events,' as defined below.

Classification	Definition
Serious Adverse Event (SAE)	
A SAE is defined in accordance with ISO 14155 as an AE that:
 
 
a. Led to death
 
b. Led to serious deterioration in the health of the participant, that either resulted in 
 
1. A life-threatening illness or injury, or
 
2. A permanent impairment of a body structure or a body function, or
 
3. Inpatient or prolonged hospitalization, or
 
4. Medical or surgical intervention to prevent life-threatening illness or injury or permanent impairment to a body structure or a body function,
 
 
 
c. Led to foetal distress, foetal death or a congenital abnormality or birth defect
 
 
NOTE: Planned hospitalization for a pre-existing condition, or a procedure required by the protocol, without serious deterioration in health, is not considered an SAE.

Adverse device effect (ADE)	An adverse device effect (ADE) is defined in accordance with ISO 14155 as "an adverse event related to the use of an investigational medical device." This definition includes any AEs resulting from insufficient or inadequate instructions for use, deployment, implantation, installation, or operation, or any malfunction of the investigational medical device as well as any event resulting from use error (per ISO 62366) or from intentional misuse of the investigational medical device.
Unanticipated Adverse Device Effect (UADE)	An unanticipated adverse device effect (UADE) is defined in accordance with 21 Code of Federal Regulations (CFR) 812.3 as "any serious adverse effect on health or safety or any life-threatening problem or death caused by, or associated with, a device, if that effect, problem, or death was not previously identified in nature, severity, or degree of incidence in the investigational plan or application (including a supplementary plan or application), or any other unanticipated serious problem associated with a device that relates to the rights, safety, or welfare of subjects."
Serious adverse device effect (SADE)	A serious adverse device effect (SADE) is defined in accordance with ISO 14155 as "an adverse device effect that has resulted in any of the consequences characteristic of a serious adverse event."

AE classification, coding (for reporting to the sponsor) and examples are provided in the following table of Contact Lens Adverse Event Classification and Reporting table:

Code	Condition	Potential AE Classification	Reporting
01	Presumed infectious keratitis or infectious corneal ulcer	SERIOUS	

02	Permanent loss of $\geq$ 2 lines of best spectacle corrected visual acuity (BSCVA)	SERIOUS	Notify sponsor as soon as possible, within 24 hrs; Independent Ethics Committee reporting as per requirements
03	Corneal injury that results in permanent opacification within central cornea (6mm)	SERIOUS	
04	Uveitis or Iritis (e.g. presence of anterior segment inflammation as described in ISO 11980, Annex B)	SERIOUS	
05	Endophthalmitis	SERIOUS	
06	Hyphema	SERIOUS	
07	Hypopyon	SERIOUS	
08	Neovascularization within the central 6mm of cornea	SERIOUS	
00	Other serious event	SERIOUS	
11	Peripheral (outside central 6mm), non-progressive, non-infectious ulcer	SIGNIFICANT	Notify sponsor as soon as possible, within 5 working days; Independent Ethics Committee reporting as per requirements
12	Symptomatic corneal infiltrative event	SIGNIFICANT	
13	Superior epithelial arcuate lesions (SEALs) involving epithelial split	SIGNIFICANT	
14	Corneal staining $\geq$ dense coalescent staining up to 2mm in diameter (e.g. moderate, ISO 11980 grade 3)	SIGNIFICANT	
15	Corneal neovascularization $\geq$ 1.0mm vessel penetration (e.g. $\geq$ ISO 111980 Grade 2), if 2 grade change from baseline	SIGNIFICANT	
16	Any temporary loss of $\geq$ 2 lines BSCVA for $\geq$ 2wks	SIGNIFICANT	
17	Any sign and/or symptom for which participant is administered therapeutic treatment or which necessitates discontinuation of contact lens wear for $\geq$ 2 weeks	SIGNIFICANT	
10	Other significant event	SIGNIFICANT	
21	Conjunctivitis (bacterial, viral or allergic)	NON-SIGNIFICANT	Notify sponsor as soon as possible, within 5 working days; Independent Ethics Committee reporting as per requirements
22	Papillary conjunctivitis if $\geq$ mild scattered papillae/follicles approximately 1mm in diameter (e.g. ISO 11890 Grade 2), if 2 grade change from baseline	NON-SIGNIFICANT	
23	Asymptomatic corneal infiltrative events	NON-SIGNIFICANT	
24	Any sign and/or symptom for which temporary contact lens discontinuation for $>$ 1 day is recommended (if not already classified)	NON-SIGNIFICANT	
20	Other sign and/or symptom warranting classification as a non-significant adverse event	NON-SIGNIFICANT	

#### 9.1.2 NORMAL OR ADAPTIVE SYMPTOMS

Transient symptoms such as end-of-day dryness, contact lens awareness, itching or burning or other discomfort may occur with contact lens wear and may occasionally reduce wearing time. These are not reported as adverse events unless in the investigators' opinion they are unexpected in nature, severe or have a high rate of occurrence.

This clinical study will also ascertain satisfaction or preference with participative attributes such as comfort, vision, or contact lens handling. Responses to these participative questionnaires will not be considered as adverse events, complaints or device malfunctions.

